3.2. Outcome Measures

Outcome measures:

- Symptom measurement (reduced Neuropsychiatric Inventory (NPI) score; lower unified Parkinson's disease rating scale score; lower Cornell depression score, Geriatric Depression Scale)
- Patient quality of life (patient EQ-5D-5L and carer proxy EQ-5D-5L for incapacitated patients; patient DEMQOL and carer DEMQOL-proxy scales)
- Carer stress and quality of life (carer EQ-5D-5L; HADS; and Zarit burden scale)
- Time spent caring for the person with dementia
- Changes in management (including changes in prescribed medication)
- Rates of cognitive decline (MMSE; and MoCA)
- Global outcomes (observer and carer rated)
- Health economic measures:
 - Primary and secondary health care resource use, use of personal social services
 - Cost to primary and secondary health care and personal social services
 - Patient costs (time and travel costs of accessing health care services)
 - Unpaid costs to carers based on the time spent caring for the person with dementia
 - Patient quality adjusted life years (QALYs) estimated from patient responses to the EQ-5D-5L and DEMQOL, and carer responses to proxy EQ-5D-5L and the DEMQOL-proxy measures, respectively
 - Carer QALYs estimated from carer responses to a carer's EQ-5D-5L

- Incremental cost per QALY gained calculated from the total costs and QALYs of the patient and the carer in order to compare the new assessment and management toolkit with usual care

4. TRIAL DESIGN

A pilot cluster randomised controlled trial (cRCT) design will be used to test the management toolkit. Participating services will be cluster randomised with half implementing the management toolkit (intervention arm) and half implementing usual clinical care (control arm). The study team will disseminate the management toolkit to the clinical teams in the intervention arm and provide appropriate training. Clinicians will use the toolkit as part of their clinical management of LBD patients according to their clinical judgement.

The study will be discussed and consent taken from the patient (or consultee) and the carer/informant for the additional study visits and for data to be collected for the study. For both arms of the study an additional visit will be arranged to conduct a baseline visit, 3 month and 6 month follow up visits.

5. STUDY DURATION AND SETTING

This is a multi-centre study with at least 8 participating services. This study will be divided into two smaller parts: a) WP5A which will involve patients from memory assessment services, (Dementia with Lewy Bodies), and b) WP5B which will involve patients from neurology and geriatric services (Parkinson's Disease Dementia).

The total study duration will be 3 years. This will include a recruitment period of 24 months, a follow up period of 6 months and a final 6 months for data analyses, interpretation and dissemination of results. Submission of abstracts will continue beyond this period to target specific conferences and publications.

The management toolkit is a recommended guideline and will be used according to clinician judgement in the intervention arm. It could be used at a single visit only, or over multiple visits/patient contacts across several months. The management toolkit will be used as part of routine practice and will remain with sites after the end of the study. Additional study visits will be conducted at baseline, 3 months and

6 months, and clinicians in the intervention arm will be asked to complete a clinician toolkit use questionnaire.

Recruitment will be reviewed at the end of month 1 and regularly thereafter at study Trial Management Meetings. The end of month 30 will be the end of the study for all participants.

6. ELIGIBILITY CRITERIA

6.1. Inclusion Criteria

Cluster randomised controlled trial to test the management toolkit:

- A clinician diagnosis of LBD has been documented as the result of specialist service assessment (possible or probable diagnosis).
- Consent can be obtained from the patient or, for those subjects lacking capacity, from a consultee.

In addition to the above criteria:

- WP5A: Patients aged 60 and over with at least 1 active clinical issue as determined by the treating clinical team;
- WP5B: Patients aged 60 and over with a diagnosis of Parkinson's disease where a memory problem has developed.

6.2. Exclusion Criteria

- Patients who have explicitly expressed a wish not to be approached to take part in research
- Patients who have been approached to take part in this study previously (as part of another participating service)
- Patients who have a severe or terminal illness and reduced life expectancy which compromises their ability to comply with the protocol
- Insufficient English to allow completion of the study measures
- Patients who are assessed as not able to complete the outcome measures for the study

Clinicians may choose not to use the management tool at some assessments if they feel it is not appropriate.

NB: Enrolling a patient onto the trial who does not meet the inclusion/exclusion criteria is considered a protocol waiver. PROTOCOL WAIVERS REQUIRE THE AUTHORISATION OF THE RESEARCH SPONSOR PRIOR TO IMPLEMENTATION.

7. TRIAL PROCEDURES

7.1. Recruitment

7.1.1. Patient Identification and Screening

Potential participants will be identified by the clinical teams, network staff or the study team through the review of medical records and patient clinic lists at the participating services. If appropriate the clinician may hand out the letter of invitation and participant information sheet at the end of the clinical appointment (e.g. if this is a diagnosis appointment). Otherwise, after the clinical appointment potentially eligible patients will be discussed with the clinician regarding mental capacity to consent for the study and the need for a consultee. Contact details will be obtained and used to send out a letter of invitation and relevant participant information sheet(s).

In all cases patients will be given a minimum of 24 hours to read the information sheet, and longer if they need time to discuss with family with whom they don't live. They will have the option to contact the team immediately if they do not wish to take part. If no objection is received, a follow up phone call will be made by the study team to arrange a study visit (either in the patient's home or in a clinical setting) to obtain consent and conduct the baseline measurements. It may not be possible for this baseline visit to be conducted before the management toolkit is used in clinical practice, but will be as soon as is reasonably and practicably possible.

A screening log will be completed to document fulfilment of the entry criteria for all patients considered for the study, including those who are subsequently included or excluded. Eligibility to the study will be confirmed by the delegated member of the study team at the baseline visit, prior to seeking consent.

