7.3. Randomisation

Participating services will be randomised to administer either the management toolkit (intervention arm) or continue with usual care services (control arm). Randomisation will be done using computer generated randomisation at a service level, stratified by site (North East and East Anglia).

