7.5. Unblinding

There will be no need for unblinding for this study, as the clinical teams involved will already be unblinded.

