9. STATISTICAL CONSIDERATIONS

9.1. Analysis Population

Within the identified services all DLB cases (existing or new diagnosis) will be identified and will be eligible for inclusion, as long as they meet the inclusion criteria. Based on a previous work package where 70 DLB subjects were identified and recruited from a similar number of services over 18 months, it is anticipated work package 5 will recruit at least 60 subjects to enter the pilot study of the management toolkit (i.e. 30 in each arm).

In an earlier work package prevalence rates of PDD to be 10% were found of all PD subjects, therefore 8 services should be sufficient to allow a similar number of PDD subjects to be recruited (60 subjects, 30 in each arm) to enter the pilot study of the management toolkit.

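### Patients are identified after services are randomised, with WP5A entry partly judged by unblinded teams, and in the intervention arm alone the baseline may follow toolkit use

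*Protocol*

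**What the plan says.** **Order of events.** Section 7.3 randomises services, not patients. Sections 4 and 7.7.1 give intervention services the toolkit and training. Section 5 sets 24 months of recruitment, followed by 6 months of follow-up.

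**Who finds and admits patients.** Section 7.1.1: "Potential participants will be identified by the clinical teams, network staff or the study team through the review of medical records and patient clinic lists". It adds: "If appropriate the clinician may hand out the letter of invitation and participant information sheet at the end of the clinical appointment". Otherwise the patient is discussed with the clinician after the appointment and the invitation is posted. A delegated study-team member confirms eligibility at the baseline visit, and everyone considered is entered on a screening log.

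**Eligibility.** Both parts need a documented clinician diagnosis of LBD, possible or probable. Section 6.1 adds for WP5A: "Patients aged 60 and over with at least 1 active clinical issue as determined by the treating clinical team". WP5B instead requires Parkinson's disease with a memory problem. Section 9.1 says that "all DLB cases (existing or new diagnosis) will be identified and will be eligible for inclusion", subject to the inclusion criteria.

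**Blinding.** Section 7.4 has measurements taken, as far as possible, by network staff unaware of allocation. Section 7.5 states that "the clinical teams involved will already be unblinded".

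**Baseline.** Section 7.1.1 says "It may not be possible for this baseline visit to be conducted before the management toolkit is used in clinical practice", and asks that the visit follow as early as practicable. Section 7.7 times the 3- and 6-month visits from that baseline. Section 7.6 records current management there, and section 3.2 lists changes in management as an outcome. Sections 3.1, 9.2 and 9.2.2 frame the hypothesis and the t-tests as change from baseline to 6 months.

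**The concern.** There are two separate problems.

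**Selection.** Randomising services makes patients comparable only if entry does not depend on allocation. In WP5A one entry criterion is a judgement by a team that knows its arm. In intervention services that team has also been trained on a guide to managing LBD problems, so it may see an active issue where an untrained team would not, or the reverse. Differences between arms at entry would then be mixed with the toolkit effect, in either direction.

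**Reference point.** A baseline taken after exposure is no longer a pre-treatment value, and this can occur in one arm only. The change score then loses whatever has already happened. Changes in management is the most exposed outcome: if the toolkit prompts a prescribing change at the appointment that leads to recruitment, the new prescription is recorded as the baseline and no change is counted.

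The pilot is meant to rehearse the analysis for a full trial (section 9.2), so a fault in the reference point would be carried forward.

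**Working it through.** The plan gives no figure on this point to reproduce. The check is first of the sequence, then of the size.

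**1. Does identification follow randomisation?** No sentence says so outright. It follows from section 7.1.1 (the toolkit may be in use before a patient's baseline), section 7.2 (consent does not alter how the service manages the patient) and section 7.8 (patients receive the toolkit or usual care whether or not they consent).

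**2. Is a post-exposure baseline a rare exception?** Both invitation routes in section 7.1.1 start at or after a clinical appointment. Section 7.7.1 describes the direct route as an appointment at which a need for management has been identified. At least 24 hours to consider and a telephone call come next, then the baseline visit. Any toolkit use at that appointment therefore precedes baseline. Existing cases are also eligible, and no limit is set on earlier exposure.

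**3. Could the overlap be measured later?** Section 7.6 and Table 1 list no date of first toolkit contact. Section 7.6 names a clinician toolkit use score, but sections 7.7.1 and 8.2 time the clinician questionnaire from service randomisation (about 6 months later, and at study end). The amendment history describes it as general, not per patient. The CRF itself is not shown.

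**4. Size of the lost effect.** Let D be the toolkit effect on the 6-month score and f the share of D already present at baseline. Assume that early exposure leaves the 6-month effect at D, that baseline and 6-month SDs are equal, and that their correlation is rho.

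- Change score: D - fD = (1 - f)D
- Baseline-adjusted: D - rho × fD = (1 - rho × f)D

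| f | Change score | Adjusted, rho 0.5 | Adjusted, rho 0.6 | Adjusted, rho 0.7 |
|---|---|---|---|---|
| 0 | 100% | 100% | 100% | 100% |
| 0.25 | 75% | 87.5% | 85% | 82.5% |
| 0.50 | 50% | 75% | 70% | 65% |

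Neither f nor rho is in the protocol; the ranges are assumptions. A definitive trial that kept this baseline practice and a change-score analysis would need 1/(1 - f)² times the sample for the same power: 1/0.75² = 1.78 times, or 1/0.5² = 4.0 times.

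**5. Selection, and why raw 6-month scores are not a cure.** Suppose selection alone produces a baseline difference of 0.2 SD (assumed).

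- If it persists in full, the raw 6-month contrast is off by 0.2 SD and the change contrast by 0.
- If it regresses with rho = 0.5, the 6-month contrast is off by 0.2 × 0.5 = 0.10 SD and the change contrast by 0.10 - 0.20 = -0.10 SD.
- With rho = 0.7 the figures are 0.14 and -0.06 SD.

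Neither contrast is safe in every case, and the sign depends on which patients are admitted.

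**The case against.** The case for leaving the plan alone has real substance.

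- **Safeguards exist.** Clinicians are not the only route in: network and study staff also search records and lists. Study staff confirm eligibility. Consent is taken only by network or study staff. Section 9.1 aims to identify all DLB cases, and the screening log covers those excluded. This limits selective entry. It does not remove the treating team's judgement of an active issue, which section 6.1 makes a condition of WP5A entry.
- **The criterion covers only half the trial.** This stands. WP5B has no active-issue requirement. That training shifts the threshold is plausible, but nothing in the protocol shows it.
- **The magnitude is assumed.** This also stands. Toolkit use is discretionary and may run over several contacts, so much of the exposure may come after baseline and f may be small.
- **It is an exploratory pilot.** Section 9.3 concedes that the sample may be too small to test the hypothesis. Consent rates, drop-out and the suitability of measures do not need an unbiased comparison between arms.
- **Sensitivity analyses may be in an SAP that is not shown.** They may be. But an SAP cannot analyse an exposure date that was never collected.

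A reader might infer that unblinded clinicians take the baseline measurements. The protocol does not support this: section 7.4 gives measurements to network staff blinded as far as possible. The lack of blinding bears on eligibility and invitation, not on scoring.

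**Conclusion.** The point holds, as a correction that should be made. Following the protocol as written, the intervention arm's baseline can contain part of the toolkit's effect. The change-score analysis would then usually be biased towards no effect, keeping 1 - f of it (75% or 50% at the assumed f of 0.25 or 0.5). Toolkit-driven changes in management made before the visit would go uncounted. Separately, WP5A patients may differ by arm because an unblinded team judges one entry criterion; neither the size nor the direction of that difference can be derived from the protocol.

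Two stronger readings are not supported. One is that the design would manufacture a false benefit: pre-baseline exposure to a helpful toolkit shrinks the change score, and selection can act either way. The other is that the pilot is invalid: its feasibility aims are untouched, and its comparisons between arms are declared exploratory.

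**What to change.** By protocol amendment:

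1. **Exposure date.** Record for each intervention participant the date of first toolkit-guided contact, and report the interval from it to baseline.
2. **Reference for changes in management.** Take medication and other management before that date from the notes. In control services use an equivalent index appointment, defined in advance (for instance, the first clinical contact after the service's allocation took effect).
3. **Analysis.** Do not label scores taken after first toolkit contact as pre-treatment. Add a sensitivity analysis limited to participants baselined before exposure, stating that this subset is itself selected and may be small.
4. **WP5A entry.** Have network or study staff, blinded where possible, apply one fixed active-issue checklist to consecutive records in both arms, and report the screening log by arm. The clinical investigators should decide its content. Staff who read intervention-service notes may learn the allocation, so they should not also be the outcome assessors.

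The cost is the amendment, one CRF field, a notes check per participant and a small extra analysis.

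Listing existing cases before allocation is released would be stronger, but it is open only to services not yet told their arm, or to the definitive trial. The October 2016 entry in the amendment history already refers to clinicians randomised to the toolkit, so for some services it is probably too late.

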7.2. Consent

Participating services will be randomised to either the intervention arm or the control arm. The cRCT design removes the need for individual participant randomisation. Consenting to the study will not affect the management method that the clinician uses as part of patient care. If the patient does not consent for any reason, the data will not be collected and used for the study and the study visit measurements will not be done.

Consent will only be taken by members of the clinical research network or study team with documented and delegated responsibility. The study team will have communicated with clinical staff ahead of the baseline study visit to assess mental capacity of the patient. Consent will be sought from the patient in the first instance whenever possible. If the patient is found to lack mental capacity, but they still appear to be willing, an opinion will be sought from a consultee. This will be the patient's carer, next of kin or nominated person as defined in the Mental Capacity Act 2015. If a patient had capacity and consented to the baseline assessment, but loses capacity during the study, then an opinion will be sought from a consultee and the patient would only continue to be included in the study if they appeared willing and the consultee agreed. If either at recruitment or at any point throughout the study, the patient appears unwilling to be included or take part in the study, then they will not be included.

Consent will be also sought from the informant/carer who is present at the visit, as they will also be acting as a participant in their own right.

The patient (or consultee) will provide written informed consent by completing and dating the consent form, which will be witnessed by the person who has documented and delegated responsibility to do so. The original signed consent forms will be retained in the ISF, with a copy filed in the clinical notes and a copy provided to the participant/consultee.

The right to refuse to participate without giving reasons will be respected. All participants will have the right to withdraw at any time.

The information sheets and consent form will be available only in English.

7.3. Randomisation

Participating services will be randomised to administer either the management toolkit (intervention arm) or continue with usual care services (control arm). Randomisation will be done using computer generated randomisation at a service level, stratified by site (North East and East Anglia).

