2.1. Work Packages

This overall work programme is aiming to improve the NHS care of people with dementia by increasing detection and optimising management of LBD in routine secondary care services. In order to achieve this there are a total of 5 related work packages. Although this protocol refers to Work Package 5, the other four work packages are also briefly outlined below.

Work Package 1 (WP1): This was a baseline study of current Lewy Body Dementia (LBD) diagnosis and management in memory, neurological and medical services. The proportion of cases diagnosed with DLB and PDD and their management pathways were compared to non-DLB dementia cases and PD cases without dementia, respectively.

Work Package 2 (WP2): This was a series of qualitative studies to explore and understand perceived barriers and facilitators to introducing an assessment tool and management toolkit into routine NHS practice. It examined current practice through observing clinic consultations, and conducting interviews with professionals, patients and carers.

Work Package 3 (WP3): This study involved developing an evidence based management toolkit to guide clinicians in the management of LBD. A systematic review of existing evidence was conducted and guided using a Delphi panel approach of a group of expert clinicians and PPI members.

Work Package 4 (WP4): This study brought together previously validated assessment methods into a simple LBD assessment tool suitable to use in the NHS. The assessment tool and previously developed

management toolkit were piloted in Gateshead NHS Trust. Modifications to the tools were made following feedback from staff, patients and carers.

Work Package 5 (WP5): This study involves introducing the management toolkit into routine NHS care in a minimum of 8 different services. A pilot cluster randomised controlled trial (cRCT) will be conducted to test the management toolkit. WP5A will focus on DLB and will run in memory assessment services. WP5B will focus on PDD and will run in movement disorder (neurology and geriatric) services. **This is the focus of this protocol.**

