9.2.1. Analysis of the Outcome Measures

For the exploratory analysis, T-tests will be used to compare the means of two samples when data is normally distributed and a Wilcoxon Signed test will be used to compare the medians of two samples when data is

skewed. The association of a binary outcome with a categorical predictor with 2 or more levels will be tested using the Chi-square test. As there is a single management tool covering both dementia with Lewy bodies and Parkinson's disease dementia, then it will be appropriate to undertake exploratory analysis on the combined PDD and DLB subject group.

Information on the variability of continuous variables measuring the symptoms such as neuropsychiatric inventory score will be useful in power calculations for a larger study.

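### Service randomisation is stratified by region but not by service type, so disease can be unbalanced between arms by chance

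*Protocol*

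**What the plan says.** Protocol section 4 makes the service the unit of allocation: "Participating services will be cluster randomised with half implementing the management toolkit (intervention arm) and half implementing usual clinical care (control arm"). Section 7.3 gives the method as "computer generated randomisation at a service level, stratified by site (North East and East Anglia"). Region is the only factor named.

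The source of each disease group is fixed. Section 2.1 (Work Packages) says "WP5A will focus on DLB and will run in memory assessment services", and "WP5B will focus on PDD and will run in movement disorder (neurology and geriatric) services". Section 5 repeats this division.

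On numbers, section 5 says "This is a multi-centre study with at least 8 participating services". Section 9.1 anticipates at least 60 DLB patients, 30 per arm, and for PDD says that "8 services should be sufficient to allow a similar number of PDD subjects to be recruited (60 subjects, 30 in each arm"). Section 9.3 describes 30 per arm as a rule of thumb.

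On analysis, section 9.2.1 says "it will be appropriate to undertake exploratory analysis on the combined PDD and DLB subject group", and section 9.2.2 repeats it. The methods listed are t-tests, a Wilcoxon test, chi-square tests, and a linear mixed model for group and time. No disease or service-type term is mentioned.

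**The concern.** Each service contributes only one disease, so disease is a property of the cluster. Balancing region does nothing for it. With few services, memory services can fall unevenly between arms, and movement disorder services then fall unevenly the other way.

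Two things follow. First, one disease may have far fewer than the anticipated 30 patients in one arm, which weakens the disease-specific estimates and variances that the pilot is meant to supply. Second, in the pooled comparison arm is partly mixed with disease and clinical setting. UPDRS-III is a plausible outcome for this to matter, because WP5B patients must have Parkinson's disease (section 6.1). Section 9.2 also describes the analysis as a rehearsal for the full trial, so an allocation scheme left as it stands may be carried forward.

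The stratification factor is protocol content, and section 7.3 states it. A later analysis plan can add adjustment but cannot change how services were allocated.

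**Working it through.** **The plan's own figures.** 2 × 30 = 60 DLB and 2 × 30 = 60 PDD; 60 + 60 = 120 patients; with one carer each, 240 participants. This agrees with the trial summary. The 30 is a rule of thumb, so there is no power calculation to reproduce.

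**Inputs from the protocol.** Service-level allocation, half to each arm; stratification by two regions; one disease per service type; at least 8 services.

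**Assumptions, because the protocol does not give them.** 4 memory and 4 movement disorder services; 2 + 2 in each region; 2:2 allocation within region; 60 / 4 = 15 patients per service.

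**Allocation with 8 services.** In a region with 2 memory and 2 movement disorder services, the chance that x memory services are in the intervention arm is C(2,x) × C(2,2−x) / C(4,2), that is 1/6, 4/6, 1/6 for x = 0, 1, 2. Combining the two regions:

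- total 2: (4×4 + 2×1×1)/36 = 18/36 = 50%
- total 1 or 3: 2 × (2×4×1)/36 = 16/36 = 44.4%
- total 0 or 4: 2/36 = 5.6%

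So the chance of not splitting 2:2 is 50%. A 3:1 split gives 3 × 15 = 45 v 15 DLB and 15 v 45 PDD. A 4:0 split puts all DLB patients in one arm and all PDD patients in the other.

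**Other layouts of 8 services (memory + movement disorder in each region).**

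- 3+1 and 1+3: 50% not 2:2; a complete split is impossible
- 3+3 and 1+1: 55% not 2:2; complete split 5%
- 4+0 and 0+4: balance is guaranteed, because region and service type coincide

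**16 services, 4 + 4 per region.** Per region the weights are 1, 16, 36, 16, 1 over 70. Over both regions:

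- 4:4 split: (36² + 2×16² + 2×1²)/4900 = 1810/4900 = 36.9%, so some imbalance has a chance of 63%
- 5:3 split, either way: 2 × 1184/4900 = 48.3%, about 37.5 v 22.5 patients at 7.5 per service
- 6:2 or worse: 722/4900 = 14.7%
- complete split: 2/4900 = 0.04%

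**Effect on the unadjusted pooled difference.** Let D be the DLB–PDD difference in the quantity analysed. The shift is D times the difference between arms in the share with DLB. At 3:1 this is (45/60 − 15/60) × D = 0.5 D; at 4:0 it is 1.0 D. The protocol gives no value for D. For assumed values of 0.2, 0.5 and 0.8 SD, the shift at 3:1 is 0.10, 0.25 and 0.40 SD.

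**After the fix.** If service type is also a stratifier, with two services per region-by-type cell, the 2:2 split is certain and the difference in disease mix is 0 when services recruit equally.

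**The case against.** The strongest reply is that WP5A and WP5B may be randomised separately. They are described as two parts with different services, different inclusion criteria and a separate target of 30 per arm. If half of the services in each part go to each arm, the problem disappears. This stands as a possibility. But sections 4 and 7.3 describe one randomisation of services and nowhere say that the parts are allocated separately.

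Other points also stand:

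- The probabilities depend on a layout that the protocol does not give. It is not even clear whether 8 is the total (section 5) or the number needed for PDD (section 9.1). With 16 services, severe imbalance is uncommon.
- A reader might take section 9.1 as a promise of 30 per arm. Its wording is an expectation about recruitment.
- A reader might infer that the pooled comparison is biased. The documents support only possible chance imbalance. Section 1 says that the two diseases share features and respond to similar management, and section 9.2.2 concerns change from baseline, in which differences in level partly cancel. A shift then requires the diseases to differ in six-month change.
- This is an exploratory pilot, and rates of consent and drop-out do not depend on disease balance.
- The analysis plan, not shown here, may include a disease term or separate estimates.

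None of this supplies a reason to leave service type out of the allocation.

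**Conclusion.** The point holds as a cheap and avoidable weakness in section 7.3. As written, service type and therefore disease can be unbalanced between arms by chance. Across the layouts tried in which region and service type do not coincide, the chance of an unequal split is 50% to 63%. The damaging splits are likeliest with 8 services: 44.4% for 3:1 and 5.6% for complete confounding under the 2 + 2 layout. With 16 services, 6:2 or worse has a chance of about 15%. All of these figures rest on the assumed number and placement of services, and the patient counts also on equal recruitment per service.

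Two stronger readings are not supported. The documents do not show that arm and disease are confounded in this trial, because the actual allocation is not reported. Nor would stratifying by service type secure 30 patients per arm: it balances services, and the protocol states no cap per service.

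**What to change.** If allocation is still open, amend section 7.3 so that service randomisation is stratified or constrained by service type as well as region, where the number of services per cell allows. Randomising WP5A and WP5B separately is equivalent to stratifying by type. If the region-by-type cells are too small or odd in number, give priority to service type. If the two parts are already randomised separately, one sentence saying so is enough. Section 5 should also give the number of services by type and region.

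If services are already allocated, which is possible since the current version 5.0 dates from June 2018:

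- report the actual split of services and patients by type and arm;
- include service type in the pooled model, and region if degrees of freedom allow;
- show DLB and PDD estimates separately beside the pooled one.

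The cost before allocation is a change to the randomisation program and a line of text, with no extra patients. In the analysis it is one or two cluster-level degrees of freedom: with 8 services, 8 − 2 = 6 falls to 5 with service type and to 4 with region as well. Adjustment cannot separate arm from disease after a complete split; in that case the pooled comparison should be reported as uninterpretable for effect.
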